### Encephalography (EEG)

Encephalography (EEG) with video is recommended at the time of TSC diagnosis and as clinically indicated thereafter for surveillance of seizure risk and response to treatment. EEG (60 minutes, included extended epochs of both wake and sleep states) are scheduled to be acquired at every visit, but at minimum will be performed at baseline and at end of treatment (12 months). Sites in this network will utilize identical EEG acquisition protocols and procedures established by the TSC Clinical Research Consortium that are designed to yield comparable results across different equipment platforms. Recordings will utilize 21 gold-plated electrodes placed according to the International 10-20 system with a digital sampling rate at a rate of 2000Hz with no filters, displayed at an effective time scale of 30 mm/sec with 1Hz low frequency and 70Hz high frequency display filters on the left screen, and on the right screen a maximum time scale of 100 mm/sec, 30Hz low frequency filter (high pass) and 100Hz high frequency filter (low pass). These parameters were designed to yield comparable data on Stellate, Nihon-Kohden, XLTEK/Natus EEG systems throughout the consortium. Any additional EEG obtained for clinical purposes between scheduled visits will also be collected for research analysis. The digitized EEG source data will be transferred to CCHMC for central processing and analysis.

## Diffusion MRI (dMRI)

Brain MRI is recommended in TSC infants annually as standard clinical care to monitor for developing or progressing SEGA. We have developed a diffusion MRI (dMRI) protocol, that is an optimally distributed set of gradient directions and strengths, and an algorithm that identifies diffusion tensor (DTI) and diffusion compartment (DCI) parameters at every voxel from the same acquisition. Each year during clinical MRI, we will include this research dMRI sequence (scan acquisition time  $\leq 15$  minutes). The TSC Clinical Research Consortium uses human phantoms as well as ACR phantoms to align the parameters for collection of diffusion MRI data at participating sites. Such an approach has allowed us to obtain high

reproducibility across sites in previous multicenter TSC studies, including TACERN. Additionally, if a clinical MRI scan with DTI is performed prior to enrollment in the study, these scans may also be included in the planned analysis.

# **12 ASSESSMENT OF SAFETY**

Safety will be monitored using laboratory and clinical parameters at each visit and periodic phone calls as indicated in the Study Schedule (Table 3). Data will be reviewed regularly by an independent medical monitor who has no other involvement in study execution or analysis or TSC patient clinical care. In addition, a dedicated Data Safety and Monitoring Board (DSMB) will be established to protect and safeguard the interests of all study patients and to oversee trial progress. The DSMB board composition at minimum will include separate clinical specialists with experience in pediatric epilepsy, TSC clinical care, and treatment with mTOR inhibitors. The independent medical monitor also will review any serious adverse events and determine if unblinding and reporting to the FDA and DSMB is required. The DSMB will receive regular reports from the trial on any injuries or adverse events and any developments that jeopardize the continued success of the trial and integrity of the data. The DSMB will meet twice yearly to examine study data and additionally may meet on an ad hoc basis as needed. The DSMB will be provided with a summary report of all AEs, deviations and SAEs as well as safety laboratory evaluations for review during the meetings.

## 12.1 Adverse Events, Safety Evaluations, and Reporting

Baseline conditions (e.g. an elevated laboratory value) at study entry will be noted and graded per the CTCAE criteria. For the purposes of this study, an adverse event (AE) is the appearance or worsening of any undesirable sign, symptom, or medical condition occurring after beginning the study drug, whether or not considered drug related. Medical conditions/diseases present before beginning study drug are only considered adverse events if they worsen after starting study drug. Epilepsy and seizures as primary outcome of interest will not be reported as an AE unless accompanied by additional symptoms or events not ordinary in the course of epilepsy management in patients with TSC. Out of range lab results that are considered clinically significant, induce clinical signs or symptoms, or require concomitant intervention or changes in study treatment also will be reported as adverse events.

Following informed consent, all AEs will be captured, graded per the specified parameters, and assigned causality. Adverse events will be assessed in accordance with The Common Toxicity Criteria for Adverse Events (CTCAE v5.0). If the event is not found in the CTCAE criteria, the event will be captured in the "other" category of CTCAE. The occurrence of adverse events should be sought by non-directive questioning of the subject at each visit throughout the study. Adverse events may also be detected when they are volunteered by the subject during or between visits, though physical examination, laboratory tests, or other assessments. Each event should be evaluated to determine:

- 1. Severity grade: CTCAE 1-5
- 2. Relationship to study drug: suspected/not suspected
- 3. Duration: start and end dates (or ongoing at the time of study completion)
- 4. Action taken: no action taken, study drug dosage adjusted/interrupted, study drug permanently discontinued, concomitant medication taken, non-drug therapy given, hospitalization/prolonged hospitalization

5. Whether it is a serious adverse event (SAE) as defined by the FDA and described below in section 12.2.

All adverse events should be treated appropriately. If any concomitant medication or non-drug therapy is given as a result, these should be recorded on the appropriate CRF.

Once an adverse event is detected, it should be followed until resolution, with an assessment made at each study visit to make note of any changes in severity, suspected relationship to study drug, interventions require, and the outcome. In addition, all adverse events will be recorded and subjects will be followed for 30 days after the last dose of study drug. At the end of the 30-day period, the Principal Investigator will determine if the patient is stable and the tracking of ongoing AE's can be discontinued. New AEs will not be captured beyond the 30-day period. At the end of the 30-day period, AEs that have not resolved (e.g. returned to at least baseline) will be documented as ongoing.

Periodic summary reports of AEs will be provided to the independent medical monitor, DSMB, and Tavanta Therapeutics, Inc. —the supplier for TAVT-18 for this study. Patient confidentiality will be maintained at all times. No PHI will be included in AE summary reports.

All adverse events are to be reported as follows, unless they meet the definition of a Serious Adverse Event described in section 12.2:

- FDA Reporting: Annually
- DSMB: Per DSMB Charter
- IRB: Per IRB requirements
- Study sponsor, independent medical monitor, and drug supplier: Monthly

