## **5 STUDY DESIGN AND ORGANIZATION**

This trial originally planned to use a two stage, phase I clinical trial design, with the first stage to employ an open-label clinical trial design to verify dosing for TAVT-18 (sirolimus) powder for oral solution in TSC infants (N=5) that would then be carried forward to inform appropriate initial dosing, dosing frequency, and dosing adjustments for the second stage—a randomized, double-blind, placebo-controlled multi-site trial design—to evaluate the safety and efficacy of early sirolimus treatment to prevent epilepsy in TSC infants until 12 months of age (N=60). However, with the elimination of the planned second stage which has now been replaced by STOP2B: TSC-STEPS, the study design now consists of a single stage, phase I clinical trial design only. Subjects will be between 0-6 months of age at time of treatment initiation and meet clinical and/or genetic diagnostic criteria for TSC and have no prior history of clinical seizures at time of enrollment. Treatment will be continued until subjects reach 12 months of age. The TSC Clinic at Cincinnati Children's Hospital Medical Center (CCHMC) will serve as the single clinical site.

Additional key investigators of the study:

- [name] (CCHMC) will direct EEG acquisition and data transfer quality control, processing, and blinded central analysis
- [name] (UNC, Chapel Hill) will direct neuropsychological assessments and data transfer quality control, processing, and blinded central analysis
- [name] [name] (CCHMC) will direct PK/PD sample acquisition and quality control, processing, and blinded central analysis
- [name] (Boston Children's Hospital) will direct dMRI acquisition and data transfer quality control, processing, and blinded central analysis
- [name] (CCHMC) will serve as study biostatistician

Operations will be managed through the Clinical Coordinating Center (CCC) and Data Management Center (DMC) at CCHMC to ensure the optimal scientific rigor, efficient execution and management of the study, and analyses.

An independent medical monitor (MM) and Data Safety Monitoring Board (DSMB) will be established to ensure patient safety is appropriately monitored and prioritized throughout the study.

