#### 6.3 Potential Risks

EEGs are routine clinical tests that are considered safe and carry negligible risk. EEGs have a minor risk of skin irritation due to adhesive used for sensor attachment but are routinely performed as part of clinical care for subjects with TSC in this age group.

MRIs are routine clinical tests that are considered safe and carry negligible risk. For subjects with TSC in this age group, the MRI performed yearly as part of clinical care routinely includes sedation. This sedation will be extended during the research portion of the MRI for no more than 15 minutes.

For blood sample collection to measure sirolimus levels and laboratory studies, there is a minor risk of pain, bleeding, bruising, or infection. When possible, blood draws will be combined with venipuncture already being performed for clinical purposes.

As part of this study there is a minor risk for a loss of confidentiality. Good clinical practice standards and institutional rules will be observed throughout all aspects of the study to maintain subject confidentiality. No individually identifiable subject data will be distributed to non-research personnel.

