#### **TABLE 3: Schedule of Study Procedures/Events**

Neuropsych assessment 						Х	Х
Dispense Study Drug	Х	Х	Х	Х	Х		
Interim phone vists 							

Subjects may be enrolled into the study at any time between the ages of 0-6 months and will receive TAVT-18 (sirolimus) until 12 months of age. Visit window for follow-up visits is  $\pm 2$  weeks.

Includes option for additional bloodwork for exploratory measures; subjects not taking study medication within the previous 48 hours of the study visit due to AE or other reasons will not have sirolimus level assessed.

Sirolimus trough levels should be drawn in the morning, approx. 24hrs after last dose of study medication. The initial level will be drawn 7-14 days after subject has been on steady dosing and in conjunction with safety labs at each clinic follow-up visit (1,3,6,9,12 mths). Similarly, trough levels will be drawn at 7-14 days after any dose modification, until target concentration is reached. For convenience, levels can be drawn at the study center or drawn locally and sent to the reference laboratory.

Routine EEG (60 minutes duration). EEG acquisition schedule for study is consistent with current TSC clinical guideline recommendations dMRI is 15-minute add-on sequence to conventional MRI that is recommended clinically every 1-3 years in TSC.

Developmental assessment consists of TAND Checklist, VABS, and Bayley-4 at the 12 months of Age visit and TAND Checklist, VABS, Bayley-4, PLS-5, and ADOS-2 at the 24 months of Age visit

Monthly calls will occur in between in-person visits. During the first month in the study, phone calls will occur weekly.

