## 12.2 Serious Adverse Events, Safety Evaluations, and Reporting

For the purpose of this study, a serious adverse event (SAE) is defined by the FDA as one which:

- Is fatal or life-threatening
- Results in a persistent or significant disability/incapacity
- Constitutes a congenital anomaly/birth defect
- Requires inpatient hospitalization or a prolongation of an existing hospitalization (greater than 24 hours) unless the hospitalization is for:
  - Routine treatment or monitoring of the studied indication, not associated with any deterioration in condition
  - Elective or pre-planned treatment for a pre-existing condition that is unrelated to the indication under study and has not worsened since signing the informed consent
  - Treatment on an emergency outpatient basis for an event not fulfilling any of the definitions of an SAE given above and not resulting in a hospital admission
  - Social reasons and respite care in the absence of any deterioration in the patient's general condition

Every SAE, regardless of suspected causality, occurring after the subject has provided informed consent until 30 days after treatment has stopped must be reported to the sponsor within 24 hours of learning of its occurrence. SAEs will also be reported within 24 hours of learning of its occurrence to the drug supplier and medical safety monitor. The medical monitor will determine

if steps to identify and treat the SAE by study investigators are appropriate, if additional investigations are required, and if treatment unblinding or treatment discontinuation is necessary.

Any SAEs occurring after the 30-day period following end of treatment should only be reported to the sponsor and medical safety monitor if the investigator suspects a causal relationship to the study drug.

SAEs that are considered to be unexpected and at least possibly related to study drug are required to be reported to the FDA within 7 calendar days of the sponsor's initial receipt of the information if characterized as fatal or life-threatening. Non-fatal or non-life-threatening events must be reported no later than 15 calendar days after the sponsor determines that the serious suspected adverse reaction (SSAR) or other information qualifies for reporting.

All SAEs are to be reported to the IRB and the DSMB as per policy and Tavanta Therapeutics, Inc. Patient confidentiality will be maintained at all times when reporting SAE.

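### AE capture closes about 11 months before the 24-month research dMRI, so harm from that scan may go uncaptured or miss the sponsor and medical monitor

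*Combined protocol and SAP*

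**What the plan says.** Treatment has a fixed end: "Treatment will be continued until subjects reach 12 months of age" (section 5). Section 12.1 says that "all adverse events will be recorded and subjects will be followed for 30 days after the last dose of study drug", and then: "New AEs will not be captured beyond the 30-day period". For serious events section 12.2 adds: "Any SAEs occurring after the 30-day period following end of treatment should only be reported" to the sponsor and medical safety monitor when study drug is the suspected cause. The same section has a separate line sending all SAEs to the IRB and DSMB according to policy, with no time limit and no causality condition written.

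Table 3 marks dMRI at 12 and 24 months. Its Adverse Event Review row is marked at 12 months and blank at 24. Section 11.6 says: "Each year during clinical MRI, we will include this research dMRI sequence". Table 3, footnote 4, says: "dMRI is 15-minute add-on sequence to conventional MRI that is recommended clinically every 1-3 years in TSC". Section 6.3 states that the yearly clinical MRI in this age group routinely includes sedation, and adds: "This sedation will be extended during the research portion of the MRI for no more than 15 minutes".

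The causality item listed in section 12.1 is relationship to study drug, suspected or not suspected. No item covers relationship to a study procedure.

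**The concern.** The safety window is tied to drug exposure, but the drug is not the only research exposure. The extra sedation time exists only because the child is in the study, and its second scheduled occasion falls long after the window has shut. About 11 months off drug, an airway or other sedation event would ordinarily be attributed to the procedure, and the late-SAE rule does not cover that attribution.

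At stake is oversight of a risk that the protocol itself names: whether the sponsor and the medical monitor would learn of it, and whether minor events would be graded and counted at all. The planned efficacy and drug-safety analyses are not affected.

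**Working it through.** The plan states no figure to reproduce. The check is date arithmetic followed by a comparison of the sections.

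**Inputs**
- End of treatment: 12 months of age, taken as day 365 (section 5).
- AE follow-up: 30 days after the last dose (section 12.1).
- 24-month visit: taken as day 730 (Table 3).
- Visit window: ±14 days at each visit (section 11.5 and Table 3).

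**Gap**
- AE capture closes at 365 + 30 = day 395, or 395/365 × 12 = 13.0 months of age.
- Gap to the 24-month visit: 730 − 395 = 335 days, or 335/365 × 12 = 11.0 months.
- Shortest: (730 − 14) − (395 + 14) = 716 − 409 = 307 days.
- Longest for a child treated to the 12-month visit: (730 + 14) − (395 − 14) = 744 − 381 = 363 days.
- If study drug stops early, the gap is longer.

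No combination of windows brings the 24-month scan inside the AE window. For a child treated to 12 months, the 12-month scan is inside it. With five infants and two scheduled scans each, at most 5 of 10 scans fall outside.

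**Where an event at the 24-month scan would go**

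| Event | Rule | Result |
|---|---|---|
| Non-serious | 12.1 cut-off | Not captured as an AE |
| Serious, study drug suspected | 12.2 late-SAE rule | Sponsor and medical monitor; IRB and DSMB under policy |
| Serious, study drug not suspected | 12.2 late-SAE rule | Not to sponsor or medical monitor; IRB and DSMB under policy |

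**Text that conflicts with the cut-off**
- Section 11.5 calls for phone contacts at least monthly for the whole study, with documentation of any interval AE not yet reported.
- Section 12 says that the DSMB receives regular reports on any injuries or AEs.
- Section 12.1 says that AEs are sought at each visit throughout the study, and defines an AE without regard to drug causality.

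The 24-month visit is a study visit, so these sentences, read literally, reach it. The cut-off sentence excludes it. A site cannot follow both.

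**Whether the scan is done at 24 months**
Table 3 marks it, and section 11.6 implies it by adding the sequence each year. The text on the 24-month visit, in the follow-up and post-treatment follow-up parts of section 11.5, lists developmental assessment and interval history but not dMRI.

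**The case against.** The strongest reply is that the cut-off sentence does not stand alone. Section 12.2 keeps a line sending all SAEs to the IRB and DSMB. Sections 11.5, 12 and 12.1 contain the broader wording set out above, and Table 3 schedules interval history, vital signs and examination at 24 months. A reader might infer from the cut-off that capture at the second scan is zero, or that no SAE could reach the DSMB. The documents do not support either inference.

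A reader might also infer from footnote 4 that a 24-month sedation could be wholly for research. That does not follow. Sections 6.3 and 11.6 and the footnote itself all describe dMRI as an addition to a clinical MRI, and no stand-alone research scan is provided for. Annual imaging in infants and imaging every 1 to 3 years in TSC generally are also not plainly contradictory. The consequence is rather that some children may have no 24-month dMRI.

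Three further points are fair. A blank Table 3 cell is weak evidence by itself: AE Review is also blank at 7–14 days, where section 11.2 requires AE collection. A procedural event can be entered as not suspected for study drug. And a window tied to drug exposure is a legitimate choice for the drug-safety endpoint.

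What remains is this. The cut-off in section 12.1 is an explicit rule and does not rest on the blank cell. The IRB and DSMB line depends on a policy that is not in the documents and does not cover non-serious events. Section 12 also has the medical monitor decide whether an SAE must go to the FDA and DSMB, while section 12.2 keeps late SAEs not attributed to the drug from that monitor. Nothing requires an event noted in the 24-month history to be graded, attributed or reported as an AE. An entry of not suspected does not show that a research procedure was the cause.

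**Conclusion.** The point holds as a conflict between sections with a practical consequence. Following the stated cut-off would lose non-serious procedure-related events at the 24-month dMRI and keep serious ones not attributed to study drug from the sponsor and medical monitor. The scan falls about 11 months after closure, at most once per infant.

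The conclusion rests on three assumptions: that the 24-month dMRI is performed, as Table 3 shows; that it is done under sedation, which is inferred from section 6.3 and not stated for that visit; and that the site follows the explicit cut-off over the broader wording. The documents give no sedation event rate, and with n=5 few events are expected. The case for the change is cheap protection of participants, with no effect on any planned analysis.

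**What to change.** 1. Reconcile sections 11.5, 12, 12.1 and 12.2 so that AEs and SAEs related to a research procedure are captured through the 24-month visit, and reported to the sponsor, medical monitor and DSMB, whatever their relation to study drug. The 30-day limit can stay for all other events.
2. Add an AE Review mark at 24 months in Table 3.
3. Add an item to the AE form for relationship to a study procedure.
4. Make the text on the 24-month visit and on post-treatment follow-up agree with Table 3 on whether dMRI is done, and say there that it is an add-on to a clinical MRI.

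The cost is amendment wording, one CRF field and slightly more AE review at an existing visit. No visit or test is added. Where no clinical MRI is due at that age, the 24-month dMRI will be missing, which already follows from its status as an add-on.

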## 12.2 Serious Adverse Events, Safety Evaluations, and Reporting

For the purpose of this study, a serious adverse event (SAE) is defined by the FDA as one which:

- Is fatal or life-threatening
- Results in a persistent or significant disability/incapacity
- Constitutes a congenital anomaly/birth defect
- Requires inpatient hospitalization or a prolongation of an existing hospitalization (greater than 24 hours) unless the hospitalization is for:
  - Routine treatment or monitoring of the studied indication, not associated with any deterioration in condition
  - Elective or pre-planned treatment for a pre-existing condition that is unrelated to the indication under study and has not worsened since signing the informed consent
  - Treatment on an emergency outpatient basis for an event not fulfilling any of the definitions of an SAE given above and not resulting in a hospital admission
  - Social reasons and respite care in the absence of any deterioration in the patient's general condition

Every SAE, regardless of suspected causality, occurring after the subject has provided informed consent until 30 days after treatment has stopped must be reported to the sponsor within 24 hours of learning of its occurrence. SAEs will also be reported within 24 hours of learning of its occurrence to the drug supplier and medical safety monitor. The medical monitor will determine

if steps to identify and treat the SAE by study investigators are appropriate, if additional investigations are required, and if treatment unblinding or treatment discontinuation is necessary.

Any SAEs occurring after the 30-day period following end of treatment should only be reported to the sponsor and medical safety monitor if the investigator suspects a causal relationship to the study drug.

SAEs that are considered to be unexpected and at least possibly related to study drug are required to be reported to the FDA within 7 calendar days of the sponsor's initial receipt of the information if characterized as fatal or life-threatening. Non-fatal or non-life-threatening events must be reported no later than 15 calendar days after the sponsor determines that the serious suspected adverse reaction (SSAR) or other information qualifies for reporting.

All SAEs are to be reported to the IRB and the DSMB as per policy and Tavanta Therapeutics, Inc. Patient confidentiality will be maintained at all times when reporting SAE.

